## 6.5 Dose escalation and dose modification

### 6.5.1 Dose modifications

The starting dose for erenumab is 70 mg/1 mL and matching placebo is 1 mL. Subjects will keep this dose throughout the study. Study treatment dose adjustments are not permitted. For subjects who are unable to tolerate the protocol-specified dosing scheme, dose interruptions of study treatment are permitted in order to keep the subject on study drug. These changes must be recorded on the appropriate CRF.

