**Table 8-1 Assessment Schedule**

Period	Screening		Double-Blind Treatment 				Post Double-Blind Treatment Follow-Up 				Open-Label Treatment 					
	Visit Name	Screening	Baseline	Day 1	Week 4	Week 8	End of Treatment (EOT)	Week 4 FUP 	Week 8 FUP 	Week 12 FUP 	Safety Follow -Up 	Week 12	Week 16, 20, 28, 32, 40, 44...	Week 24	Week 36, 48, and every 12 weeks	End of treatment Open-label
Days	-42	-28	Day 1	28	56	84		28	56	84	140	84	112, 140, 196, 224, 280, 308...	168	252, 336...	
Weeks	-6	-4	1	4	8	12		4	8	12	20	12	16, 20, 28, 32, 40, 44...	24	36, 48...	
Vital signs and body measurements 	X	X	X	X	X	X		X	X	X	X					
Chemistry	X		X				X				X			X		
Hematology	X		X				X				X			X		
Pregnancy Test (serum)	X						X									
Pregnancy test (urine)		S	S	S	S			S	S	S	S			S	S	S
Urine Drug Screen	X															
Anti-AMG 334 antibodies 			X				X				X					
eDiary Dispensing		S														
eDiary Return 			S	S	S	S		S	S	S						
Clinical Outcome Assessment(s)			X 					X 								

Period	Screening		Double-Blind Treatment 				Post Double-Blind Treatment Follow-Up 				Open-Label Treatment 					
	Visit Name	Screening	Baseline	Day 1	Week 4	Week 8	End of Treatment (EOT)	Week 4 FUP 	Week 8 FUP 	Week 12 FUP 	Safety Follow-Up 	Week 12	Week 16, 20, 28, 32, 40, 44...	Week 24	Week 36, 48, and every 12 weeks	End of treatment Open-label
Days	-42	-28	Day 1	28	56	84		28	56	84	140	84	112, 140, 196, 224, 280, 308...	168	252, 336...	
Weeks	-6	-4	1	4	8	12		4	8	12	20	12	16, 20, 28, 32, 40, 44...	24	36, 48...	
Concomitant medications	X	X	X	X	X	X	X	X	X	X			X	X	X	X
Concomitant therapies	X	X	X	X	X	X	X	X	X	X			X	X	X	X
Adverse Events 	X	X	X	X	X	X	X	X	X	X						
Study drug administration 			X	X	X							X	X	X	X	
Study Disposition Form						X					X					X

X Assessment to be recorded in the clinical database or received electronically from a vendor

S Assessment to be recorded in the source documentation only

 All study visit target dates are to be calculated from the Day 1 visit date, and all study procedures for a given visit should be completed in the same day.

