 Entry (i.e. randomization) into the double-blind treatment period using the IRT System must occur only after the successful completion of all Screening Period requirements and prior to the first dose of study drug (randomization and administration of the first dose must occur on Day 1).

 Week 4 FUP, Week 8 FUP, Week 12 FUP are to be performed by discontinued subjects (double-blind treatment period) who are willing to remain on the study to perform regular assessments.

 The Safety Follow-Up Visit is required for all subjects who either discontinue study drug in the double-blind treatment period or complete the double-blind treatment period without continuing in the open-label treatment period. Safety Follow-Up Visit is 12 weeks after last dose of study treatment during the double-blind treatment period. For patients discontinuing treatment during the double-blind treatment period and remaining on the study to follow the assessment schedule until Week 12 Follow-Up (FUP) visit, Safety Follow-Up visit should occur on Week 20 even if last dose was taken at Day 1.

 Sites will access the Interactive Response Technology (IRT) System to enter the subject into the initial screening period, to randomize an eligible subject into the

double-blind treatment period, to dispense study treatment during the double-blind and open-label treatment periods, and to register study early termination. Subject data will be collected in the IRT System including, but not limited to, reason for screen fail (if applicable). The IRT system will automatically assign study drug when a subject is randomized.

 Including prior prophylactic migraine medication

 Height collected at Screening visit only. Weight collected at Screening, Baseline, and End Of Treatment (double-blind treatment period) visits. Blood pressure, pulse and body temperature collected at every double-blind treatment period visit.

 At Day 1 visit sample should be collected prior to dose administration.

 Subject brings the eDiary device to each double-blind treatment visit for use at site.

 Subjects will record headache and headache medication information daily, using the provided eDiary device, during the double-blind treatment period.

 Completed daily via the eDiary device, during the double-blind treatment period.

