2.1.1.1 Study dates

eDiary Device Assignment Date

The date on which an eDiary device is assigned to a subject for the first time after completion of initial screening at week -4 visit.

Randomization (Enrollment) Date

Randomization (Enrollment) Date is the date on which a subject is assigned to one of the treatments through IRT in DB period.

First DB IP Dose Date

The first DB IP dose date is the date on which a subject is administered the first dose of IP following randomization, which may be the same day (most of the time) or after the randomization date. For subjects who are randomized but never dosed with double-blind IP after randomization, First DB IP Dose Date is considered missing.

Last DB IP Dose Date

The last DB IP dose date for each subject is defined as the latest date IP is administered during DB period.

First OLE IP Dose Date

The first OLE IP dose date is the date on which a subject is administered the first OLE dose of IP on or after Week 12. The first OLE IP dose date will only be applicable for subjects who enter OLE period.

Last OLE IP Dose Date

The last OLE IP dose date for each subject is defined as the latest date IP is administered during OLE period, which is applicable for subjects who enter OLE period.

Subject-level End of DB Treatment (EOT DB) Date

The end of DB treatment date for each subject is defined as the end of the treatment in DB period. The date will be recorded on the Treatment disposition eCRF page.

Subject-level End of OLE Treatment (EOT OLE) Date

The end of OLE treatment date for each subject is defined as the end of the treatment in OLE period. The date will be recorded on the Open-label Treatment disposition eCRF page.

Subject-level End of Study (EOS) Date

The end of study (EOS) date for each subject is defined as the last date on which the subject participated in the study. The date will be recorded on the Study disposition eCRF page.

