Monthly efficacy measurements will be calculated based on the subject's monthly investigational product (IP) dosing schedule defined below using eDiary data collected from beginning of the baseline period (Week -4 visit) up to the End of Treatment in DB period (Week 12 visit).

Table 2-3 Study Intervals for Efficacy Endpoints

Study Phase	Assessment Time point	Interval Based on Dose Dates	
		Start date	End date
Baseline Period	Baseline	From eDiary device assignment date (or Week -4 visit)	Day prior to study day 1
DB Period	Week 4	Study Day 1	
• Week 4 dose date-1• Study day 28 if Week 4 dose is not received (either missed or IP discontinued prior to Week 4) 
Note: if day 1 dose is the last IP dose subject received, the rest of monthly assessments during treatment period will be calculated based on consecutive 28-day interval beginning on study day 29 (ie, 29-56 for week 8, 57-84 for week 12)

	Week 8	
• Week 4 dose dateStudy day 29 if Week 4 dose is not received (either missed or IP discontinued prior to Week 4)	
• Week 8 dose date-1Study day 56 if Week 8 dose is not received (either missed or IP discontinued prior to Week 8)
	Week 12	
• Week 8 dose dateStudy day 57 if Week 8 dose is not received (either missed or IP discontinued prior to Week 8)	
MIN (Study day 84, EoS) if Week 8 dose is not received
 
MIN (Week 8 dose date + 28, EoS) if week 8 dose is received

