The number of subjects with PDs according to the applicable SOP will be presented for DB Period. The results of the PDs will be grouped using the broad categories defined in the applicable SOP, which currently are:

- Eligibility: Subject did not satisfy entry criteria
- Withdrawal: Subject developed study/treatment withdrawal criteria during the study, but was not withdrawn
- Study Drug: Subject received the wrong treatment or incorrect dose
- Concomitant Medication: Subject took a prohibited concomitant medication
- Other GCP deviation

A complete list of the PDs can be found in the Edit Check Specifications document in CREDI.

Subjects with PDs and non-PDs leading to data exclusion from analysis sets will be listed.

To evaluate the impact of COVID-19 on trial integrity, the number of subjects randomized during COVID-19 pandemic period, the number of subjects under DB period during COVID-19 pandemic, as well as the number of subjects who reported COVID-19 related PDs during DB period will be summarized.

The COVID-19 related PDs will be grouped in summary by following categories which was defined by clinical trial team with reference to COVID-19 guidance released by Novartis:

- Missed visit due to COVID-19
- Visit done outside of study site due to COVID-19
- Assessment/procedure changed due to COVID-19
- Non-compliance with baseline period duration due to COVID-19
- Non-compliance with no re-screening post-baseline failure due to COVID-19
- Discontinuation due to COVID-19
- Treatment not given or delayed due to COVID-19
- Changes in drug supply method (self-administration) due to COVID-19

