5.1.5 Other imputations

5.1.5.1 eDiary data

The eDiary includes the following clinical outcome assessments:

- Incidence of headache (i.e., migraine with or without aura or non-migraine headache)
- Time of onset of headache
- Time of resolution of headache
- Pain severity per headache
- Symptoms (e.g., nausea, vomiting, photophobia, phonophobia)
- Presence of aura
- Acute medication taken to treat headache, aura-only event, or both headache and aura

As well as, subject-reported outcomes (PROs) measures of [REDACTED], modified MIDAS, [REDACTED], [REDACTED]

Missing eDiary data in the calculation of monthly measurements about subjects' migraine and non-migraine headaches will be handled using the following method:

1. For monthly intervals with ≥ 14 days of eDiary days (including retrospective eDiary days) in each interval:
 - a. Monthly frequency measurements (including migraine days, [REDACTED], migraine attacks, acute medication use, acute migraine specific medication use etc.) will be prorated to 28-day equivalents. Prorated result does not need to be rounded.
[REDACTED]
2. For monthly intervals with < 14 days of eDiary use (including retrospective eDiary days), all monthly measurement will be set as missing and will be handled as described in [Section 5.1.5.3](#).

Briefly, handling missing and incomplete eDiary data is summarized by next rules:

Monthly Endpoint	Condition	Proration Method (does not need to be rounded)
------------------	-----------	--

Monthly frequency measurements (including migraine days, [REDACTED] acute headache medication treatment days)	If diary days in entire baseline or interval post baseline ≥ 14 (including retrospective eDiary days), then do proration; Else monthly measurement is set to missing [diary days is a day with all headache related questions completed retrospectively or not]	Number of observed migraine days * 28/ Number of information days in interval [information day is a diary day or headache day]
[REDACTED]	[REDACTED]	[REDACTED]

Missing PROs [REDACTED] mMIDAS [REDACTED] scheduled to be collected at office visit at certain assessment will not be imputed.

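### SAP Table 2-3 starts the Week 12 interval at the actual Week 8 dose, but the diary stops at a visit targeted from Day 1, so a very late dose can cost a recorded primary value that a missed dose would keep

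*SAP*

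**What the plan says.** **Interval limits (SAP 2.1.3, Table 2-3).** The Week 12 interval begins on the actual Week 8 dose date and ends at "MIN (Week 8 dose date + 28, EoS) if week 8 dose is received". If the Week 8 dose is not received, the interval is Study Days 57–84, cut at end of study if that is earlier. The Week 8 interval ends the day before the Week 8 dose.

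**Where the diary stops.** The sentence introducing the table uses eDiary data only "up to the End of Treatment in DB period (Week 12 visit"). Protocol Table 8-1, footnote 11, has subjects record headaches daily "using the provided eDiary device, during the double-blind treatment period".

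**Meaning of EoS.** SAP 2.1.1.1 has the subject's end of study "defined as the last date on which the subject participated in the study". That is not the Week 12 visit.

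**Visit anchor.** Protocol Table 8-1, footnote 1: "All study visit target dates are to be calculated from the Day 1 visit date".

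**Short intervals (SAP 5.1.5.1).** With 14 or more diary days, counts are prorated to 28 days. With fewer, "all monthly measurement will be set as missing". The primary analysis does not impute (SAP 2.5.3), and the 50% responder analysis scores a missing value as non-response (SAP 2.6.3).

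**Late doses are foreseen.** Protocol 6.7.2 sets a ±5-day tolerance and asks for sponsor discussion outside it, without barring such doses. Protocol 6.5.1 says "dose interruptions of study treatment are permitted in order to keep the subject on study drug". SAP 2.3.1 has a deviation category "Treatment not given or delayed due to COVID-19".

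**The concern.** The interval and the diary run on different clocks. A late Week 8 dose moves the start of the primary window but not the target date of the visit that closes the diary. The window then shrinks from the front, whatever the subject's diary compliance. Past a certain delay it drops below the 14-day minimum and the Week 12 value is set to missing.

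The result is perverse. Two subjects can have identical, complete diaries through Day 84. The one who never received the Week 8 dose keeps a 28-day primary value, and the one dosed very late has none. The SAP has no rule for when a late dose counts as not received, so that choice could be made after data are seen.

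At stake are the Week 12 values of monthly migraine days, of acute headache medication days (which use the same intervals), and of the 50% responder endpoint. A late Week 4 dose shortens the Week 8 interval in the same way.

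The end-date cell is also unclear in itself. It refers to end of study where the lead-in refers to the Week 12 visit. Dose date + 28 also spans 29 inclusive days, against 28 in the fallback.

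**Working it through.** **Inputs.** Visit targets are Days 28, 56 and 84 (Protocol Table 8-1; SAP Table 2-2). The minimum is 14 diary days (SAP 5.1.5.1). Dosing tolerance is ±5 days (Protocol 6.7.2). Response rates in the earlier chronic migraine trial are 39.9% for 70 mg and 23.5% for placebo (Protocol 1.1). Design values are a difference of −2.0 days, SD 6.8, 550 subjects, 10% dropout and a final two-sided threshold of 0.046 (Protocol 12.8.1).

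**The plan's own figures.**
- Fallback interval: 84 − 57 + 1 = 28 days, as intended.
- Sample size: 243 per arm for 90% power at 0.05, so 486 in total, and 486 / 0.9 = 540, close to 550.
- Power: with 550 × 0.9 = 495 evaluable, it is 90.5% at 0.05 and 89.9% at 0.046, which matches the protocol's approximate 90%.

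**Usable diary days.** For a Week 8 dose on Day 56 + d and a Week 12 visit on Day V, counting the visit day:

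days = min(56 + d + 28, V) − (56 + d) + 1

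For V = 84 this is 29 − d. For V = 79 it is 24 − d.

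| Days late (d) | Visit Day 79 | Visit Day 84 | Visit Day 89 |
|---|---|---|---|
| 0 | 24 | 29 | 29 |
| 5 | 19 | 24 | 29 |
| 10 | 14 | 19 | 24 |
| 11 | 13 (missing) | 18 | 23 |
| 15 | 9 (missing) | 14 | 19 |
| 16 | 8 (missing) | 13 (missing) | 18 |

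If the visit day is not counted, lengths drop by one and most thresholds come one day earlier.

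**Incomplete diary.** At 80% completion and V = 84, d = 11 gives 0.8 × 18 = 14.4 days (kept) and d = 12 gives 0.8 × 17 = 13.6 days (missing).

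**Where the skipped days go.** Days 57 up to the day before the late dose fall in the Week 8 interval, which ends at the Week 8 dose date − 1. They stay in the repeated-measures model under Week 8.

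**Size, under an assumed 2–5% loss of Week 12 values, equal in both arms.**
- Responders: the difference is 39.9 − 23.5 = 16.4 points. Non-response scoring removes 0.02 × 16.4 = 0.3 to 0.05 × 16.4 = 0.8 points.
- Power at 0.046: 89.9% with 495 values, 89.3% with 2% lost (485) and 88.4% with 5% lost (470). The fall is 0.6 to 1.5 points.

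**The case against.** The case for leaving the table alone is substantial.

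- **Dose-anchored months are deliberate.** SAP 2.1.4.1 defines monthly migraine days between doses, normalized to 28 days. This stands, and nothing here requires abandoning it.
- **The loss needs a long delay.** A reader might infer that any late dose deletes the endpoint. The documents do not support that: in-tolerance doses keep 24 or more days with the visit on Day 84, and 19 with it on Day 79. Such windows are prorated, so the cost is some precision and a shift in the period measured.
- **The visit can also move.** Only its target is fixed. Protocol Section 8 asks for visits as close to target as possible, and SAP Table 2-2 accepts Week 12 assessments on Days 72–99. A late visit restores days, as the Day 89 column shows.
- **A very late dose may be handled as missed.** Table 2-2 ends Week 8 at Day 71, and a dose on Day 72 is exactly d = 16. But Table 2-2 governs laboratory, vital-sign and questionnaire visits, not dosing, and the SAP states no such rule for doses.
- **Data are not simply discarded.** This stands. Pre-dose days go to the Week 8 interval, subjects still contribute Weeks 4 and 8, and multiple imputation and baseline-carried-forward sensitivity analyses are planned (SAP 2.5.4).
- **Unequal loss by arm is speculative.** Interruption for intolerance could cause it, but Protocol 1.1 describes tolerability similar to placebo, and a skipped dose triggers the Day 57–84 fallback.
- **A separate derivations document exists.** SAP 2.1.4.1 refers to one. It may cover late doses, but it is not available here.

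**Conclusion.** The mechanism is real and its reach is narrow. With the Week 12 visit on Day 84, a complete diary loses its primary value only from 16 days late. At 80% completion this happens from 12 days, and for a complete diary with the visit on Day 79 from 11 days. A missed dose keeps Days 57–84. The Week 12 end date and the lead-in also need reconciling.

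The documents do not give the frequency of such delays. The 2–5% behind the 0.3–0.8 responder points and 0.6–1.5 power points is an assumption, and it would have to consist of doses at least 11–16 days late. One might be tempted to quote the effect on the erenumab response rate alone, 0.02 × 39.9 = 0.8 to 0.05 × 39.9 = 2.0 points. Non-responder scoring applies to both arms, so that overstates the change in the comparison.

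Nothing here threatens the primary conclusion. This is a cheap improvement: it keeps recorded data and settles in advance when a dose counts as missed.

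**What to change.** Amend SAP Table 2-3 before unblinding. Dosing and visits are untouched.

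1. For interval derivation only, treat a Week 4 or Week 8 dose given more than 5 days after its 4-week target as not received, for both intervals that meet at that dose. For the Week 4 dose the boundary becomes Day 28/29. For the Week 8 dose it becomes Day 56/57, with the Week 12 interval ending on Day 84. Resetting both sides keeps the intervals contiguous.
2. When the Week 8 dose is received within that limit, end the Week 12 interval at MIN(Week 8 dose date + 27, double-blind End of Treatment visit). This gives 28 days and replaces the reference to end of study.
3. Apply both rules to every monthly endpoint derived from daily eDiary entries, and check them against the separate derivations document.

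The cost is a few lines of SAP text and a small programming change. There are three downsides. For late-dosed subjects the final window includes some days before the late dose, as it already does for missed doses. There is a step at the cut-off: a dose on Day 61 starts the window on Day 61, and a dose on Day 62 starts it on Day 57. After an early dose on Day 51 the window would end on Day 78 rather than Day 79, leaving one more day before Day 84 outside any interval.

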#### **6.7.2 Instruction for prescribing and taking study treatment**

Subcutaneous (s.c.) injections are to be administered in the clinic by qualified staff at drug dispensing visit.

For purposes of study treatment dosing, “q.m.” refers to an every 4 weeks injection regimen. The study drug administration date should be in 4-week increments ( $\pm$  5 days) from the first dose of study drug. Any dose administrations that may occur greater than  $\pm$  5 days from the 4-week timepoint (e.g. subject unavailability) should be discussed with the Sponsor prior to dosing. The anatomical sites for administration of investigational product are the upper arm, upper thigh, or abdomen; the location of the injection sites should be documented in the source document.

One injection will be administered by qualified study staff at each dosing visit during the 12-week treatment period (i.e. at Day 1 and Weeks 4 and 8). Subjects will be administered one of the following, depending on their randomization:

- 70 mg erenumab: one 70 mg erenumab syringe
- Placebo: one placebo syringe

One injection of 70 mg erenumab will be administered by qualified study staff at each visit during the open-label treatment period.

The investigator must promote compliance administering the study treatment exactly as prescribed. The investigational product dose is fixed and will not be adjusted for individual subjects during the study. There are no temporal restrictions for study drug administration (eg, proximity to meals, sleep or activity).

All kits of study treatment assigned will be recorded in the IRT, both for the double-blind treatment and the open-label treatment period. Novartis monitors will reconcile treatment assigned vs treatment administered and ensure that the information is congruent during their monitoring visits.

During the COVID-19 pandemic:

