2.1.4 Definition of terms included in study endpoints

2.1.4.1 Efficacy endpoints

Please refer to the document “Important derivations in AMG” (in CREDI: AMG334A/Administrative files/CIS (Clinical Information Sciences)/Biostatistics) for more detail on the derivations. Derivations will be based on eDairy data and done by analysis team.

eDiary Day

A day in which a subject uses the eDiary.

Information Day

A day which is either a headache day or an eDiary day.

Migraine Day

A migraine day is defined as any calendar day in which the subject experiences a qualified migraine headache (onset, continuation, or recurrence of the migraine headache). Please see exceptions in [Appendix 5.10](#). A qualified migraine headache is defined as a migraine with or without aura, lasting for ≥ 4 continuous hours, and meeting at least one of the following criteria:

1. ≥ 2 of the following pain features:

- Unilateral
- Throbbing
- Moderate to severe
- Exacerbated with exercise/physical activity

2. ≥ 1 of the following associated symptoms:

- Nausea and/or vomiting
- Photophobia and phonophobia

If the subject took ANY acute medication (simple analgesics [NSAIDs, acetaminophen], combination analgesics, triptans or ergot-derivative) during aura, or to treat a moderate or severe headache on a calendar day, then it will be counted as a migraine day regardless of the duration and pain features/associated symptoms. Opioid-containing analgesic and butalbital-containing analgesic are excluded in allowed acute medication categories.

Monthly Migraine Days

Number of migraine days between each monthly IP dose that are normalized in a 28-day interval. Monthly migraine days at baseline are the number of migraine days in the baseline period that are normalized in a 28-day interval. Days without eDiary data in each normalized monthly interval will be prorated. All details of calculation are in [Section 5.1.5](#) (The same proration method will be applied for other efficacy endpoints thereafter).

Modified Migraine Disability Assessment (mMIDAS)

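### SAP Table 2-3 gives subjects who received the Week 8 dose a 29-day Week 12 window for the primary endpoint, ending on schedule on the End of Treatment visit day; the end date should be dose date + 27

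*SAP*

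**What the plan says.** SAP Table 2-3 sets the eDiary windows behind monthly migraine days (MMD) and the other monthly efficacy measures. Baseline stops the day before Study Day 1. The Week 4 and Week 8 windows stop the day before the next dose, or on Day 28 or Day 56 if that dose was not received.

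The Week 12 window has two end rules. Without a Week 8 dose it starts on Day 57 and ends at "MIN (Study day 84, EoS) if Week 8 dose is not received". With a Week 8 dose it starts on the dose date and ends at "MIN (Week 8 dose date + 28, EoS) if week 8 dose is received". A note in the table gives subjects dosed only on Day 1 a "consecutive 28-day interval beginning on study day 29 (ie, 29-56 for week 8, 57-84 for week 12"). The sentence introducing the table limits the eDiary data to those collected "up to the End of Treatment in DB period (Week 12 visit").

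SAP Section 2.1.4.1 defines MMD as the "Number of migraine days between each monthly IP dose that are normalized in a 28-day interval". SAP Section 5.1.5.1 gives the proration: observed migraine days × 28 / information days. For exposure, SAP Section 2.1.1.3 takes the minimum of the last double-blind dose date + 27, the End of Treatment (EOT) visit and the cutoff date. SAP Section 2.1.1.1 defines EoS as the subject's last date in the whole study.

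**The concern.** The rule that covers most subjects, and that defines the primary endpoint window, is one day longer than the table's own 28-day convention. It also lacks the step back of one day that closes the earlier dose-based windows.

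The added day is not an arbitrary one. On schedule it is the Week 12/EOT visit, and Protocol Section 8.4.3 treats that visit as the first open-label visit for subjects who continue. For a subject who rolls over without a gap, a placebo subject included, it is the day of the first open-label erenumab injection. The only cap in the cell, EoS, cannot remove that day for an open-label entrant, because EoS then falls after open-label treatment.

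At stake are the exact definition of the primary endpoint, the responder and acute-medication endpoints built on the same windows, and agreement between the sponsor's programmers and the external team that produces the unblinded interim output.

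**Working it through.** **1. The table's counting convention.** Length = end − start + 1.
- Days 29-56: 56 − 29 + 1 = 28.
- Days 57-84: 84 − 57 + 1 = 28.

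Both match the 28 days stated in the table's note, so both end dates are counted.

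**2. The Week 12 window with a Week 8 dose on day D.** From D to D + 28: (D + 28) − D + 1 = 29 days.
- Dosing every 28 days from Day 1 puts the Week 8 dose on Day 57: Days 57-85, 29 days.
- Nominal target days (SAP Table 2-2) put it on Day 56: Days 56-84, 29 days.
- With + 27 the windows are Days 57-84 and Days 56-83, 28 days each.

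**3. What falls on day D + 28.** Protocol Section 6.7.2 says "The study drug administration date should be in 4-week increments" (± 5 days) from the first dose, and the first footnote to Protocol Table 8-1 says "All study visit target dates are to be calculated from the Day 1 visit date". The scheduled Week 12 visit is therefore 28 days after the Week 8 dose, on the last day of the window.

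This depends on actual timing. If the ± 5 days also applies to the Week 12 visit (an assumption), the gap from Week 8 dose to Week 12 visit runs from 28 − 10 = 18 to 28 + 10 = 38 days.
- Visit on D + 28: the EOT day is the 29th day.
- Visit before D + 28: the table rule runs past EOT, and only the introductory sentence stops it.
- Visit after D + 28: the EOT day is outside the window, which is still 29 days long.

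**4. Effect on one subject.** Let k be the migraine days in the first 28 days, and let x = 1 if the 29th day is a migraine day and 0 if not. With a full diary:

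shift = (k + x) × 28/29 − k, which is −k/29 for x = 0 and (28 − k)/29 for x = 1.

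| k (assumed) | 29th day not a migraine day | 29th day a migraine day |
|---|---|---|
| 8 | −0.28 | +0.69 |
| 12 | −0.41 | +0.55 |
| 16 | −0.55 | +0.41 |
| 20 | −0.69 | +0.28 |
| 24 | −0.83 | +0.14 |

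**5. Effect on a responder.** Take a baseline of 16 and k = 8, exactly a 50% reduction. If the 29th day is a migraine day, MMD = 9 × 28/29 = 8.69, and the reduction is (16 − 8.69)/16 = 45.7%. The subject becomes a non-responder.

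**The case against.** The strongest reply is that the design already absorbs a day. Doses may move by ± 5 days, and baseline may last 35 days, or 50 under the COVID-19 provision, so window lengths vary between subjects by intent and MMD is prorated to 28 days. That stands. A reader might infer that the 29-day window is wrong because it differs in length between subjects, or because it alone contains a visit day. The documents do not support either: every window already starts on a visit or device-assignment day. The fault is narrower. This one cell also closes on the next visit day, against the pattern of the rows above it.

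A reader might also infer that open-label diary data flow into the primary endpoint because EoS does not bind. That goes too far. The introductory sentence stops the data at the Week 12 visit, the eDiary is kept only during the double-blind period (Protocol Table 8-1 footnotes and Section 8.5.1), and SAP Table 2-1 starts the open-label phase the day after EOT. What can enter is the EOT day itself, which is the first open-label dose day only if that dose is given at an EOT visit on or before dose + 28. Protocol Section 3 allows a gap before open-label entry.

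Finally, SAP Section 2.1.4.1 refers to a separate derivations document that is not available here and may settle the point. That would not correct Table 2-3.

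**Conclusion.** The end date for subjects who received the Week 8 dose is one day too late. It conflicts with the other endings in Table 2-3 and with the SAP's own + 27 exposure rule, and on schedule it brings the EOT visit day into the primary endpoint.

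The consequence is small. With 8 to 24 migraine days and a full diary (both assumed), one subject's MMD moves by between −0.83 and +0.69 day, and a borderline responder can change status. The rule is the same in both arms and the count is rescaled, so the expected effect on the treatment difference is near zero. Nothing here threatens power or type I error, and the point should not be read as evidence of bias in favour of either arm. It is a minor derivation error, worth correcting before unblinding because the primary endpoint depends on it.

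It would be tempting to conclude that EoS is the wrong cap throughout and that EOT should replace it in the rule for subjects without a Week 8 dose. The documents point the other way. Under Protocol Section 9.1.1, a subject who stops treatment early has EOT at the next 4-weekly visit and may stay in follow-up to Week 12. After a single dose on Day 1, EOT falls near Day 28, before the Week 12 window opens on Day 57. An EOT cap would empty the window and contradict the table's note.

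**What to change.** In SAP Table 2-3, Week 12 row, for subjects who received the Week 8 dose, replace the end date by MIN(Week 8 dose date + 27, day before the double-blind End of Treatment visit, EoS).

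Leave the end rule for subjects without a Week 8 dose, MIN(Study day 84, EoS), as it is, so that off-treatment diary data from follow-up are kept. Check that the separate derivations document and the interim team's programs use the same rule.

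The cost is one table cell and a program check. Read together with the limit already in the introductory sentence, the change drops at most one diary day per subject: the EOT day if that visit is on or before dose + 28, otherwise day + 28 itself. No new data are needed.
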